PLWH can be powerful change agents for HIV prevention within communities. Our research suggests that as PLWH receive ART and restore their health, they are motivated to protect their social network members and engage in prevention advocacy (i.e., encourage friends and family to seek HIV testing and care and reduce HIV risk); however, the quality of this advocacy is hampered by challenges related to message content, style and timing of delivery, and the selection of appropriate recipients for advocacy. With effective advocacy training, mobilizing PLWH to be change agents within their networks has the potential to be a “game changer” for HIV prevention, particularly in high-prevalence settings where virtually every family is touched by HIV. In the proposed research, we will conduct a randomized controlled trial (RCT) of *Game Changers*, an 8-session peer-led group intervention that aims to empower and mobilize PLWH to be agents for HIV prevention in their social networks. By decreasing stigma among PLWH and their social network members, as well as training PLWH on key strategies to engage social network members in discussions around HIV, *Game Changers* provides PLWH with the tools to do prevention advocacy and is facilitated by peers who are from participants’ communities and living with HIV. *Game Changers* was developed through an NIMH-funded R34 in partnership with the Infectious Diseases Institute (IDI), a public-private partnership in Kampala that provides care to PLWH, that trains healthcare workers on HIV care and treatment, and conducts research to address the HIV epidemic. As part of the intervention development process, the team conducted focus groups with PLWH and social network members, and engaged with community stakeholders, including a community advisory board. Our pilot RCT with 98 PLWH and 57 social network members revealed promising preliminary intervention effects on reduced internalized stigma and increased HIV-serostatus disclosure to social network members among PLWH, as well as increased condom use and HIV testing among social network members.

The **Specific Aims** are:

1. To conduct a fully powered RCT of *Game Changers* to test intervention effects on the primary outcomes of increased HIV testing, reduced condomless sex, and decreased enacted HIV stigma among social network members of participating PLWH.
2. To test intervention effects on the secondary outcomes of reduced internalized HIV stigma, increased HIV serostatus disclosure, and increased viral load suppression among participating PLWH, and PrEP uptake among their social network members.
3. To examine whether increased HIV prevention advocacy by PLWH mediates intervention effects on their social network members’ increased HIV testing and condom use, and whether increased HIV disclosure by PLWH mediates intervention effects on social network members’ reduced HIV stigma.
4. To conduct a cost-effectiveness analysis of the intervention.

We will recruit 210 PLWH, randomizing 105 to the intervention and 105 to a no-intervention control condition. Each PLWH will be asked to recruit social network members (up to 4, with expected average of 3.5 network members per participant) to complete assessments (736 total network members, 368/arm), and test intervention effects on social networks. All participants will complete surveys at baseline, and 6-, 12-, and 18-months post-baseline. The cost-effectiveness analysis will inform policymakers about whether *Game Changers* is a feasible intervention in which to invest.

Our approach is particularly timely in the era of biomedical interventions, which require widespread penetration of effective HIV prevention and care messaging into communities. Positioning PLWH as central to the solution for controlling (vs. causing) the HIV epidemic has the potential to reduce HIV stigma and improve prevention outcomes at the individual, household, and network levels. Consistent with theories of social diffusion, cognitive consistency, and social influence, studies show peer advocacy interventions reduce HIV risk in advocates themselves.⁶⁻¹⁰ However, with the exception of our pilot work, we are unaware of studies of the effects of prevention advocacy by PLWH with family, friends and community members. If successful, the intervention will be a significant innovation for the field, as it targets advocacy to all types of social network members rather than specific peer or risk groups, and uses social network information to strategically target advocacy.

SIGNIFICANCE

HIV Prevalence Remains High in Uganda

About 1.2 million people are living with HIV in Uganda. HIV prevalence is estimated to be 6.2% among those aged 15-64,¹ and is higher—6.9%—in Kampala, the proposed study setting.^{2, 3} In addition, 74% of people living with HIV (PLWH) know their status, 89% of those who know their status are on antiretroviral treatment (ART; 72% of all PLWH), and 78% are virally suppressed (56% of all PLWH).¹¹ A recent study of 20 Ugandan health facilities found that only 53% of newly diagnosed individuals are linked to care within 1 month.¹² Only 56% of men and 42% of women used a condom at last sex with a casual partner,¹³ and <10,000 people are estimated to be on pre-exposure prophylaxis (PrEP) through demonstration and research studies.⁴ These findings highlight the continued significant gaps in the HIV care continuum in Uganda.

Innovative, Low-Cost Strategies are Needed for HIV Prevention

[figure not shown]
In Uganda, political and cultural barriers, including limited government HIV funding and HIV stigma,⁵ have impeded HIV prevention and led to projections of rapid increases in HIV incidence.³ Innovative, easy-to-implement solutions are needed that do not depend on public resources, can reach a large number of people efficiently, and reduce stigma while promoting prevention. In the proposed research, we will conduct a randomized controlled trial (RCT) of just such an intervention, *Game Changers*, in which peers (PLWH) rather than professionally educated providers are the catalysts for change within social networks and communities. Research suggests that peer-based HIV prevention programs can be effective at increasing condom use and can be more cost effective than employing professionally educated providers; however, few rigorous effectiveness and cost effectiveness analyses exist of such interventions in developing countries.¹⁴⁻²⁰ Thus, we propose to conduct an effectiveness and cost-effectiveness analysis that will provide essential information for guiding community-based programming decisions in resource-limited settings.

Empowering PLWH to be Change Agents Draws on the Full Armament of Prevention Paradigms

Mobilizing PLWH as change agents for prevention *integrates and extends components of major prevention paradigms*: (1) advocating for protective behaviors (e.g., condom use, HIV testing, PrEP) among network members (promoting primary prevention);²¹ (2) increasing protective behaviors in PLWH advocates and their HIV-positive peers through advocacy (Prevention for Positives),²²⁻²⁴ and (3) advocating for linkage to HIV care and ART adherence among people who test positive (Treatment as Prevention).^{25, 26}

Receipt of HIV care often comes with renewed health, and our research suggests that essentially all PLWH have actively encouraged friends and family to seek HIV testing and care, and reduce HIV risk.^{27, 28} Harnessing this natural tendency for advocacy holds tremendous promise for HIV prevention in high prevalence settings such as Uganda, where every family is touched by someone living with HIV; mobilizing the >1 million Ugandans who are receiving HIV care to be change agents *can enable widespread penetration of HIV prevention messaging*. Our research indicates Ugandan PLWH have dense, interconnected networks,²⁹ and have disclosed to many people in their network,³⁰ suggesting that transfer of HIV prevention messages and knowledge can be efficient. In sum, *PLWH could become an essential part of the solution to HIV, rather than being stigmatized as the source of the problem*. PLWH have access to at-risk individuals within their networks, and are *in the position to be influential and credible in conveying prevention messages to family and friends* given their close relations, and their ability to exemplify the benefits of HIV testing and care on health.³¹

Figure 1. Conceptual Model of *Game Changers* Intervention

Prior HIV Prevention Interventions and Theories of Behavior Change provide a Solid Scientific Premise

Game Changers, which is based on recommended approaches to network-based and prevention interventions,^{32, 33} acts through individual- and dyadic-level mediators to change behaviors of both PLWH and their social network members (i.e., alters) (see Fig. 1). We start with the assumption that effective advocacy

requires coping with internalized HIV stigma and self-acceptance. Reduced internalized stigma is linked to increased HIV disclosure,³⁴ which is essential to encouraging others to engage in HIV protective behaviors. *Game Changers* provides coping strategies to navigate stigma and discrimination (effective in our prior research³⁵) through experience-sharing and role plays, and using compassion-focused therapy principles.³⁶⁻³⁹ *Game Changers* helps PLWH to reduce shame and increase self-compassion and empathy for others to reduce internalized stigma. As stigma decreases, PLWH are more comfortable disclosing their serostatus, which is part of managing stigma, gaining self-acceptance and community reintegration⁴⁰—and thus key to effective prevention advocacy. Disclosure enables a person to share their experiences of living with HIV, which raises the credibility of their advocacy, as they have experienced the consequences of risk behavior and the benefits of ART. Some may assume or speculate that a person who advocates for HIV protective behaviors is HIV-positive, so selection of targets for advocacy calls for considering whether the target knows the advocate's serostatus or whether the advocate is comfortable disclosing their status to the target. The consequence theory of disclosure⁴¹ posits that disclosure decisions involve weighing both risks and benefits. Among the benefits of disclosure is increased social support, associated with better individual health and more prosocial behaviors.⁴²⁻⁵¹ Although research in sub-Saharan Africa reveals that most responses to disclosure are supportive,⁵²⁻⁵⁴ the risk of negative responses such as rejection and abuse are real, particularly for women given the gender power differential present in African cultures.⁴¹ *Game Changers* draws on existing HIV disclosure interventions⁵⁵ using role playing and sharing of experiences to help participants develop disclosure decision-making skills and awareness of when and whom to disclose to and discuss HIV with.

Regarding dyadic-level mediators, *Game Changers* leads to increased quantity and better quality of prevention advocacy among PLWH. *Game Changers* uses adapted HIV prevention advocacy strategies from interventions such as Mpowerment,⁵⁶ and Popular Opinion Leader (POL)⁵⁷ interventions, as well as an effective intervention developed by [name] (MPI) in South Africa.⁵⁷⁻⁵⁹ Strategies include looking for “teaching moments,” (i.e., opportunities when alters seem more open to a message of behavior change such as after a radio ad for an HIV testing event), role playing how to initiate conversations about HIV, and learning effective communication skills (e.g., reflective listening; using empathy rather than confrontation).

Game Changers is innovative in its efforts to optimize information dissemination and behavior change throughout change agents' social network by encouraging PLWH to target advocacy to strategically chosen network members (most at risk; most popular/connected members; members that bridge different groups). Prior social network interventions provided less guidance about strategic alters to target for advocacy. In intervention sessions, PLWH map their own social network, identifying groups of alters, well-connected alters, and alters to whom they have disclosed as a visual tool for selecting alters for advocacy. The network map enables PLWH to understand how alters are connected (or not connected), and how advocating to alters in strategic positions could help to reduce stigma and increase protective behaviors in the network as a whole.^{60, 61} By engaging in advocacy with members who are popular or who bridge distinct network components, PLWH may be able to advocate more efficiently, as they encourage alters to share the information with others.

Our model specifies that PLWH's advocacy can result in behavior change for both PLWH and their alters. To be effective advocates, PLWH must model the behaviors they encourage others to adopt, by prioritizing healthy, positive living (e.g., condom use, ART adherence). *Game Changers* draws on evidence-based interventions designed to help PLWH live healthy lives^{62, 63} and uses role plays to build skills and self-efficacy, problem-solving techniques, and goal setting to help participants attend to their health.⁶⁴ Moreover, cognitive consistency⁶⁵ theory suggests that encouraging others to adopt a behavior increases the odds that the advocate will adopt the behavior—resulting in increased condom use and viral suppression. By engaging in prevention advocacy discussions, alters' HIV prevention behaviors are hypothesized to improve (HIV testing, and PrEP and condom use; care engagement and adherence if positive). *Game Changers* draws on social diffusion theory^{32, 66-68} and principles of social influence⁶⁹ to posit that behavior change can be initiated by a few, and diffused to others, through social norm change, by harnessing the power of people in the network whom alters see as supportive and credible,^{10, 57, 70-72} and by delivering an intervention to alters across networks.⁷³ *Game Changers* targets the HIV protective behaviors of both PLWH advocates and alters, as well as processes (disclosure, advocacy) needed to support behavior change at the individual and network levels.

INNOVATION

***Game Changers* empowers PLWH to act as change agents within their overall social network—not only with other PLWH or those in the same HIV risk group.** Other peer prevention interventions^{7, 8, 14, 31, 57, 58, 74} target specific sub-populations or high-prevalence communities and advocate to other members of the same group.^{7, 8, 14, 31, 57, 58, 74} Similarly, PLWH have been trained to advocate for HIV protective behaviors with other PLWH—but no existing program empowers and trains PLWH to engage in advocacy with both HIV-negative and -positive members, peers and non-peers, in their social network, to disseminate prevention

advocacy widely. *Game Changers* takes the unique perspective that all PLWH can be trained to be agents of change, regardless of their position in the community. With essentially every family and network affected by a PLWH in high prevalence settings like Uganda, *Game Changers* has the potential to dramatically impact the epidemic through its emphasis on targeting advocacy across the whole network. *Game Changers* is one of the few network-based interventions that uses information about one's social network to teach participants how to strategically select network members for advocacy. During the intervention, participants easily create their own network diagram on paper and are told how to identify alters who bridge network clusters or who are most connected, to more efficiently reach individuals throughout the network and obtain greater network change.

Game Changers catalyzes behavior change throughout the HIV prevention and care continuum among individual PLWH and their alters. Most HIV prevention and adherence interventions focus on change of one behavior at the individual level (e.g., adherence counseling in one-on-one sessions). By including both PLWH and their alters, and integrating and extending each major HIV prevention paradigm currently in play (as described above), *Game Changers* can improve outcomes from HIV prevention to care. Prior social network interventions for HIV prevention have produced mixed results, with some studies showing beneficial effects for both those engaging in advocacy⁹ and network recipients of the advocacy,^{6, 7, 10} and a recent systematic review revealed significant effects on sexual health behaviors,⁷⁵ but some interventions have resulted in no or weak effects.^{70, 75} Further, few social network interventions have been scaled up in the real world, though low resource settings may be the most cost effective context for such interventions, as networks could help maximize efficient spread of information and behavior change.⁷³ Our pilot work (see Preliminary Studies) suggests *Game Changers* leads to behavior change among both PLWH and their alters. Thus, *Game Changers* is unique, efficient, and potentially cost-effective in its multi-level, multi-behavior focus, requiring only the cost of training and paying peer facilitators to spread HIV prevention messages to the community.

Game Changers addresses HIV stigma at multiple levels. Few stigma reduction interventions have been effective, and few studies have measured their structural effects, such as on social networks. One effective intervention mobilized healthcare providers to reduce HIV stigma among other healthcare providers, but did not examine effects on their social networks (e.g., family, friends).⁷⁶ By increasing open discussions about HIV across social networks within communities, *Game Changers* may contribute to stigma reduction.

APPROACH

Preliminary Studies

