*Game Changers Pilot RCT.*⁸³ 98 PLWH and 57 alters participated in the pilot RCT across four intervention-control cohorts (with a wait-list control group).⁸³ The pilot intervention was the same as the intervention outlined below for the proposed study. Participants were interviewed at baseline and ~5-months and ~8-months post-baseline. Results showed high feasibility, acceptability, and preliminary effects, consistent with our conceptual model. In terms of feasibility, of the 98 participants recruited (51 intervention, 47 control), 97 (99%) and 93 (95%) completed assessments at months 5 and 8, demonstrating very high retention. Retention was also high in intervention sessions, with 60% of the intervention group attending all sessions and each session attended by an average of 76% of participants. Reasons for missed sessions included being out of town, conflicting work/school schedules, sick or caring for someone sick, moved, and transportation issues.

To test the feasibility of recruiting alters, we asked each of the 98 PLWH to refer up to 3 alters; 214 alters were referred by 89 (91%) PLWH (average of 2.3 alters (out of max. of 3) referred by each, suggesting little difficulty in identifying alters to recruit). However, since alter recruitment was added post-hoc to the study design (and with no designated funding in the budget), we decided to try to contact only 135 alters. Of the 135 alters, 17 (13%) were already enrolled (15 as PLWH, 2 as alters) and thus were ineligible, and 1 was withdrawn. Of the remaining 117, 34 (29%) could not be reached (did not answer the phone or had a nonworking number); and 26 (22%) declined because they were busy, lived far, or were sick. Thus, 57 alters (49%) were enrolled; 35 from intervention participants and 21 from control participants. The characteristics of the recruited alters (61% female, 32% family, 68% friends, 14% sex partners; 43% HIV+) were similar to that of all alters listed in the index participant networks (53% female, 37% family, 63% friends, 4% sex partners; 28% HIV+), which increases confidence that the recruited alters represent the larger network. We did not repeatedly

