Assessment: Overview. Under the leadership of [name] (MPI), the assessment was developed to include individual-level survey questions for PLWH and alters, and a social network assessment for PLWH only. The 60-75 min. assessment for PLWH and 20-minute assessment for alters will be administered at baseline and months 6, 12, and 18. The 6-month interim period is consistent with the Ugandan Ministry of Health recommendation for repeated HIV testing every 6 months (one of our primary outcomes), and the 18-month follow-up period will allow us to better assess durability of effects. Participants will receive 30,000 Ush (~\$8) per assessment, and 30,000 Ush (~\$8) transportation reimbursement for each intervention session. We will collect tracking information (phone numbers, mapped addresses, contacts for family/friends with whom they have frequent contact). Clinic staff, including “Linkage Facilitators” (i.e., expert patients identified by IDI clinic staff who track patients) will help to track patients that we have difficulty reaching (if participants consent). In our other 12-month longitudinal studies of PLWH in Uganda, we have achieved $\geq 90\%$ retention, and retention in our R34 pilot was $> 95\%$ for both PLWH and alters at the final month-8 follow-up. Assessments will be administered on laptops using Egoweb,¹⁰¹ social network and survey data collection and analysis software developed at RAND. The assessments include the following sections, which we have refined across multiple studies in the US and Uganda (and translated into Luganda; alphas below provided from Ugandan studies).

Individual-Level Outcomes. Sexual Behavior (condomless intercourse) in the past 6 months will be assessed with standard items on number of partners; number of times engaged in intercourse (vaginal or anal) and of those, number of times a condom was used; and perceived HIV serostatus of partner(s).

Alters' HIV Testing (among alters of negative or unknown serostatus) will be assessed. At every time-point, alters will report whether they have been tested for HIV and if so, the date of their most recent test and result,¹⁰⁰ and whether they intend to get tested in the next 6 months (1, not at all, to 5, very much) or start HIV care and ART (if warranted). Self-reported HIV testing and status has been found to be reliable.¹⁰¹⁻¹⁰⁴

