Statistical Power. We calculated power for alter reports of condomless sex at month 18. Based on the pilot, we assume 65% of control alters will report condomless sex at month 18. Starting with 736 alters, and assuming ~15% attrition by month 18 (which is conservative, based on 98% alter retention over 8 months in the pilot, and <10% attrition over 12 months in our other studies in Uganda), we will have 625 alters; accounting for within-ego clustering gives us an effective sample size of 612 for ICC=.01 or 568 for ICC=.05. For ICC=.01, we will have .80 power to detect a group difference of 10.3% (i.e., an intervention rate of 54.7%), and for ICC=.05, we will have power to detect a 10.7% group difference. These differences represent small effect sizes (Cohen's $d = .23\text{--}.24$). For PLWH index participants, using pilot data, we estimate the ICCs of our secondary outcomes to be small-to-moderate (0-.16), and assume 15% attribution and 7 intervention groups (either Game Changers or attention control), with an average cluster size of 12.9 (90 intervention participants/7 groups).^{96, 140, 141} After accounting for within-group correlations, we will have 80% power to detect medium to large differences (.41-.58 SD, based on the outcome) between the study arms at follow-up.

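### Aim 1 calls the trial fully powered for three primary outcomes, but power is shown only for condomless sex; HIV testing has a smaller denominator and enacted stigma has no stated basis for a power figure.

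*Combined protocol and SAP*

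**What the plan says.** Specific Aims, Aim 1, promises "To conduct a fully powered RCT" and names the "primary outcomes of increased HIV testing, reduced condomless sex, and decreased enacted HIV stigma among social network members".

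The Statistical Power section gives one calculation for a primary outcome: "We calculated power for alter reports of condomless sex at month 18". Its inputs are "we assume 65% of control alters will report condomless sex at month 18" and "Starting with 736 alters, and assuming ~15% attrition by month 18". It arrives at 625 alters, an effective sample size of 612 (ICC .01) or 568 (ICC .05), and detectable differences of 10.3 and 10.7 points, described as d = .23–.24. Its second calculation concerns secondary outcomes of the index participants (PLWH) and gives "medium to large differences (.41-.58 SD, based on the outcome").

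Three other places bear on the two remaining primaries:

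- Individual-Level Outcomes restricts the alters' HIV-testing outcome to those "among alters of negative or unknown serostatus".
- The pilot RCT section describes the recruited alters as "14% sex partners; 43% HIV"-positive, and gives 28% HIV-positive among all listed alters.
- The Social Network and Network Composition sections have each PLWH list 20 alters and report, alter by alter, on stigmatizing behaviour.

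No control rate, denominator, ICC or detectable difference is given for HIV testing or enacted stigma.

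**The concern.** The claim covers three outcomes and the evidence covers one. That would matter little if the condomless-sex calculation carried over to the others, but for HIV testing it cannot. That calculation uses every retained alter, whereas the testing outcome leaves out HIV-positive alters, a large group in the pilot. Enacted stigma comes from a different informant, with a different cluster structure, so the figure does not carry over there either.

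Interpretation is at stake. A null result on HIV testing from a trial described as fully powered could be read as evidence against small effects of the size quoted for condomless sex, when the design may have only about 60–70% power for effects of that size.

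**Working it through.** **Assumptions not in the documents.** Alpha and sidedness are not stated; I use two-sided 5% (z = 1.96) with 80% power (z = 0.842). Everything is at a single time point, as in the plan's own calculation. HIV-positive shares are pilot values, not trial assumptions. Control testing rates are illustrative.

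**1. Reproduce the plan's alter figures.**
- Retained: 736 × .85 = 625.6.
- Alters per PLWH: 625/210 = 2.98. Design effect = 1 + (2.98 − 1) × ICC = 1.020 (ICC .01) or 1.099 (ICC .05).
- Effective N = 612.9 and 568.8 (stated 612 and 568).
- Detectable d = 2 × (1.96 + 0.842)/√N = .226 and .235 (stated .23–.24).

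These agree. The difference in proportions does not. For 65% vs 54.7% with 306 per arm:
- d√n = .103 × √306 = 1.802
- 1.96 × √(2 × .5985 × .4015) = 1.359
- √(.65 × .35 + .547 × .453) = .689
- Power = Φ((1.802 − 1.359)/.689) = Φ(.643) = .74, not .80.

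The detectable fall at 80% power is 11.1 points. For ICC .05, 10.7 points at N = 568 also gives .74, and the detectable fall is 11.5 points. The stated 10.3 and 10.7 points match a rise from 65% (power .797 and .799), which is opposite to the hypothesis. One-sided 5% would give .83.

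**2. HIV testing on its own denominator.**
- 43% HIV-positive: 736 × .85 × .57 = 357; 357/210 = 1.70 per PLWH; design effect 1.007–1.035; effective N 354–345.
- 28% HIV-positive: 736 × .85 × .72 = 450; 450/210 = 2.14 per PLWH; design effect 1.011–1.057; effective N 445–426.

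Detectable d uses the formula in step 1. Power at d = .235 is Φ(.235 × √N/2 − 1.96). Detectable rises in points solve the two-proportion pooled-variance formula for 80% power.

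| | 43% HIV-positive (N 345–354) | 28% HIV-positive (N 426–445) |
|---|---|---|
| Detectable d | .30 | .27 |
| Power at d = .235 | .59–.60 | .68–.70 |
| Points from 10% control | 10.7–10.9 | 9.4–9.6 |
| Points from 20% control | 13.1–13.3 | 11.6–11.9 |
| Points from 50% control | 14.7–14.9 | 13.1–13.4 |
| Points from 80% control | 10.5–10.6 | 9.5–9.7 |
| Power for pilot contrast, 20.0% vs 33.3% | .80–.81 | .88–.89 |

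Reaching d = .23–.24 needs an effective N of about 594–546.

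These figures, like the plan's, count only clustering within the referring PLWH. The Aims 1–3 analysis also allows for correlation within session groups, which would lower the power.

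**3. Enacted stigma.** Retained PLWH: 210 × .85 = 178.5. With 20 reported alters each there are 3,570 reports, and effective N = 3,570/(1 + 19 × ICC), where ICC is the correlation among one reporter's reports.

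| Within-reporter ICC | .05 | .10 | .20 | .30 | .50 |
|---|---|---|---|---|---|
| Detectable d | .13 | .16 | .21 | .24 | .30 |

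One summary score per PLWH gives 2 × 2.802/√178.5 = .42. If only the 3.5 enrolled alters per PLWH were used, d = .23–.24 would require an ICC of at most about .02–.06. All of this is before session-group clustering.

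**The case against.** The plan ties d = .23–.24 to condomless sex alone and never promises it for testing or stigma, so missing it is not an arithmetic error. That is right. The fault is a claim wider than its support, and d = .23–.24 serves only as a yardstick.

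The testing shortfall also depends on thin inputs. The 43% comes from 57 pilot alters whose recruitment was added after the design was set, and the trial changes how alters are chosen. Control testing rates are unknown; low or high rates shrink the detectable difference to about 9–11 points. The repeated-measures model could alter precision. All of this stands, and it is why the result is a range.

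Three stronger readings are tempting and should be resisted.

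- A reader might infer that enacted stigma also falls short, at .41–.58 SD. The plan gives that range for secondary PLWH outcomes with session-group clustering. Stigma is collected for each of 20 alters and the analysis allows for correlation within a PLWH's alters, so reports need not collapse to one value per PLWH. Stigma could beat d = .23–.24 or miss it.
- A reader might infer that the trial cannot detect the pilot's testing effect. It would have about .80–.89 power for that contrast before session-group clustering, although the contrast is 5 of 15 against 1 of 5.
- A reader might infer that condomless sex, at least, is shown to be fully powered. The stated rates do not reproduce .80 under a two-sided 5% test.

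**Conclusion.** The concern holds in limited form. The fully powered claim is supported by a calculation for one of three primary outcomes, and that calculation does not transfer to the others.

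- **HIV testing:** detectable d is about .27–.30, with power of about .59–.70 at d = .235. This is a moderate shortfall that rests on pilot HIV-positive shares of 28–43%, ICC .01–.05, 15% attrition and a two-sided 5% test at one time point.
- **Enacted stigma:** power is undetermined. The documents fix neither the unit of analysis, the score nor the within-reporter ICC, so neither adequacy nor inadequacy can be asserted.
- **Condomless sex:** the claim should not be carried forward unchecked, given about .74 power at the stated rates.

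**What to change.** In Specific Aims (Aim 1) and Statistical Power:

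1. Remove the blanket description of the trial as fully powered, and do not keep it for condomless sex until 65% vs 54.7% has been recalculated with alpha and sidedness stated.
2. Add the detectable difference for HIV testing on alters of negative or unknown serostatus, stating the assumed HIV-positive share and control rate. Under the pilot shares this is d of about .27–.30: about 12–13 points from 20%, 13–15 from 50%, and 9–11 from 10% or 80%. Say whether session-group correlation is included.
3. Define the unit, endpoint and ICC for enacted stigma, then state its detectable difference. Do not carry over .41–.58 SD.

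The cost is revised wording and a few added figures, with no added participants. The downside is that the stated power becomes less favourable.
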